STUDY SUMMARY

Title of the clinical investigation

Evaluation of the feasibility of an expert patient decision-support system for optimizing the management of conditionally administered medications in a surgical ward

Short title

MORPHEE-2

Sponsor

Strasbourg University Hospitals

Principal Investigator

[name] [name]

HUS No.

8706

IDRCB No.

2022-A01926-37

Clinical Trial No.

NCT05707247

Rationale for the clinical investigation

The management of the numerous medications prescribed in connection with a surgical procedure represents a major challenge. Many new drugs are prescribed simultaneously, some of which are administered on an “as needed” basis, leading to a risk of suboptimal administration. The development of expert systems providing patient decision support represents a promising approach to improving perioperative medication management.

Primary Objective

To evaluate the feasibility of the INSAMED computerized decision-support tool regarding the administration of “as needed” medications after surgery.

Secondary Objectives

1. To evaluate the time to administration, according to current organizational practices, of medications prescribed on an “as needed” basis after surgery, in order to confirm the relevance of developing expert systems to improve current practice.
 2. To assess patient satisfaction with the therapeutic response provided as part of routine care.
 3. To assess patient satisfaction regarding the ease of use of the investigational device.
 4. To assess the safety of the recommendations generated by the computerized tool.
-

Primary Evaluation Criterion

Rate of concordance between the recommendations provided by the INSAMED computerized tool and those established by healthcare professionals.

Recommendations generated by INSAMED will be collected through extraction of the usage history from the digital interface (commercial smartphone) hosting the expert system.

Recommendations established by a healthcare professional based on a best-practice algorithm will be determined after receipt of an activation message from the device: a research nurse (RN) will generate a recommendation based on the medical algorithm for symptom management, medical prescriptions, and patient interview, without consulting INSAMED.

Secondary Evaluation Criteria

1. **Time delay**, in minutes, between the patient’s request for a nurse according to usual practice (e.g., call bell) for pain, nausea/vomiting, or constipation, and administration of the therapeutic response.
This delay will be recorded by the research nurse. The patient will simultaneously contact the ward nurse (call bell) and activate INSAMED, which will record the time of request.
2. **Patient satisfaction** with the therapeutic response provided by the ward nurse, measured using a visual analog scale from 0 to 100. Patient satisfaction will be analyzed according to whether there is concordance or discordance between the INSAMED recommendation and the nurse’s response.

3. **Patient satisfaction** regarding the ease of use of the INSAMED device, measured using a visual analog scale from 0 to 100.
 4. **Grading of potential harm** associated with discrepancies between INSAMED recommendations and those established by the research nurse, according to the National Coordinating Council for Medication Error Reporting and Prevention (NCC MERP) scale, adapted into three levels.
-

Study Design

Prospective, single-center pilot study.

Inclusion Criteria

- Male or female aged 18 years or older (no upper age limit)
 - Undergoing surgery in a surgical department of Hautepierre Hospital, Strasbourg University Hospitals
 - Able to read and understand French
 - Neurosensorially capable of interacting with a tactile graphical interface
 - Able to understand the objectives and risks of the research and provide dated and signed informed consent
 - Affiliated with a social security health insurance scheme
-

Non-Inclusion Criteria

- Patients with neuropsychiatric or sensory disorders likely to interfere with use of the visual interface
 - Inability to provide informed information (emergency situation, comprehension difficulties, etc.)
 - Pregnant or breastfeeding women (self-reported)
 - Patients under legal protection (guardianship, curatorship, or judicial safeguard)
-

Practical Conduct of the Study

Information and Inclusion Visit (V0)

- Anesthesia consultation or pre-anesthesia visit
- Signing of informed consent
- Training in the use of the INSAMED device

Visits V1 and V3: Day 0 +1 and Day 0 +2 (morning)

- Provision of the INSAMED device
- Reminder regarding its use

Vx: In case of pain, nausea/vomiting, or constipation

- Activation of INSAMED by the patient
- Call to the ward nurse for effective symptom management
- Patient answers INSAMED questions
- INSAMED: recommendation based on a programmed algorithm
- Visit by the research nurse (without access to INSAMED) 60 minutes after activation; the device sends an email alert upon activation
 - Recommendation based on a standard medical symptom treatment algorithm, medical prescriptions, and patient interview

The patient will be managed according to routine care recommendations, without consideration of INSAMED recommendations.

Visits V2 and V4: Day 0 +1 and Day 0 +2 (evening)

- Retrieval of the INSAMED device

Investigational Medical Device

The investigational medical device is a software prototype. It consists of a patient interface designed to assist patients with the administration of “as needed” medications in the postoperative period. The device is presented in the form of a smartphone with a tactile interface.

Participating patients are invited to activate the device when experiencing one of the following symptoms: pain, nausea/vomiting, or constipation. The device then asks the patient questions via the visual interface, to which the patient responds. The device subsequently issues a recommendation.

This recommendation is not communicated to the ward nurse responsible for patient care, who continues treatment according to routine care practices. The smartphone hosting the software is a CE-marked commercial smartphone manufactured by Samsung or Apple.

Authorized and/or Prohibited Medications/Treatments

Prescriptions will be made in accordance with routine practice. No treatment is prohibited.

Number of Subjects Required

30 subjects

The required number of subjects for this pilot study was set at 30 based on pragmatic feasibility considerations and in accordance with empirical rules described by Arain. Additionally, as data are repeated for each of the 30 subjects, the statistical power will be greater than that of a test conducted on 30 subjects without repeated measures.

If a patient never activates the device, an additional patient will be included until 30 patients have activated the device at least once. Therefore, the required number of subjects corresponds to the number of subjects who have used the device at least once, not the number of subjects enrolled, which is expected to be higher.

To achieve this objective, **60 patients are targeted for inclusion.**

Statistical Methods

Statistical analysis will include an initial descriptive phase (mean, median, standard deviation, and interquartile range for quantitative data; counts and percentages for qualitative variables).

Analysis of the primary endpoint will consist of evaluating concordance between the application's recommendation and that of the research nurse. As these are repeated binary data, concordance will not be assessed using a kappa coefficient, but rather through calculation of an intraclass correlation coefficient (ICC) derived from a mixed-effects logistic regression model with a random subject effect. Residual variance will be indirectly estimated using the methods described by Chakraborty et al.

The ICC will be reported with its 95% confidence interval, without formal hypothesis testing, as this is a pilot study.

Projected Timeline

- **Inclusion period duration:** 12 months
- **Participation duration per subject:** 2 days to a maximum of 2 months
- **Total study duration:** 14 months
- **Exclusion duration:** Not applicable

End of the research

The end of the research corresponds to the last visit of the last subject participating in the study.

Version 1.2 dated 20/12/2022, approved by the CPP Île-de-France II on 09/01/2023 and submitted to the ANSM on 13/01/2023

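### The primary concordance measure has no direction and no correction for chance, so a high figure need not show that INSAMED can tell when not to give an as-needed drug

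*Combined protocol and SAP*

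**What the plan says.** Under Primary Evaluation Criterion the endpoint is "Rate of concordance between the recommendations provided by the INSAMED computerized tool and those established by healthcare professionals". No section lists the possible recommendations, says when two of them count as concordant, or distinguishes one kind of disagreement from the other.

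A pair of recommendations exists only after an activation. Under Investigational Medical Device: "Participating patients are invited to activate the device when experiencing one of the following symptoms: pain, nausea/vomiting, or constipation". Under Practical Conduct of the Study, the same event triggers "Call to the ward nurse for effective symptom management", and the reference recommendation comes later: "Visit by the research nurse (without access to INSAMED) 60 minutes after activation; the device sends an email alert upon activation".

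Statistical Methods states: "As these are repeated binary data, concordance will not be assessed using a kappa coefficient". The replacement is an "intraclass correlation coefficient (ICC) derived from a mixed-effects logistic regression model with a random subject effect", and "The ICC will be reported with its 95% confidence interval, without formal hypothesis testing, as this is a pilot study".

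Secondary criterion 4 is the only other place where disagreements are examined. It is headed "Grading of potential harm" and applies a three-level adaptation of the NCC MERP scale to discrepancies between INSAMED and the research nurse.

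**The concern.** INSAMED is meant to help with as-needed drugs, where a central question is whether to give something at all. Every episode in the primary analysis starts with a patient who reports a symptom and asks for help. If 'give' is the common answer in such episodes, two sources can agree often without the tool discriminating between episodes. A plain agreement figure cannot reveal this, and the plan sets kappa aside without putting another chance-corrected or direction-specific measure in its place.

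The two kinds of discordance also carry opposite meanings. INSAMED giving where the nurse would withhold points to over-treatment relative to the reference; the reverse points to under-treatment. The endpoint scores them identically. A reader of the final report could not tell whether the tool errs in one direction, nor how it performs in the episodes where the nurse would not give.

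**Working it through.** **Figures in the plan.** There is no expected concordance, target, margin or 'give' share. The 30 device users are a pragmatic number, so there is no calculation to reproduce. Everything below rests on assumed shares.

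**Notation.** p_D and p_N are the shares of activations in which the device and the nurse say 'give'. Po is observed concordance.
- Chance agreement under independence: Pe = p_D·p_N + (1 − p_D)(1 − p_N).
- Kappa = (Po − Pe)/(1 − Pe).

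**Step 1. Give/withhold scoring, equal shares p (assumed), observed concordance 90% (assumed).**

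| p | Pe = p² + (1 − p)² | Kappa at Po = 0.90 |
|---|---|---|
| 0.50 | 0.25 + 0.25 = 0.50 | 0.40/0.50 = 0.80 |
| 0.70 | 0.49 + 0.09 = 0.58 | 0.32/0.42 = 0.76 |
| 0.80 | 0.64 + 0.04 = 0.68 | 0.22/0.32 = 0.69 |
| 0.90 | 0.81 + 0.01 = 0.82 | 0.08/0.18 = 0.44 |
| 0.95 | 0.9025 + 0.0025 = 0.905 | −0.005/0.095 = −0.05 |

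The same 90% is good agreement at the top of the table and no better than chance at the bottom.

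**Step 2. A tool that always says 'give'.** With p_D = 1, Po = p_N and Pe = p_N, so kappa = 0. This does not need the independence assumption. Concordance equals the nurse's 'give' share, so it is 80-95% if that share is 80-95%.

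**Step 3. Direction.** Assume 30 patients with 3 activations each, so 90 pairs, of which 9 are discordant. Concordance is 81/90 = 90% whether all nine are 'INSAMED gives, nurse withholds' or all nine are the reverse. This holds whatever the 'give' share.

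**Step 4. Conditions that lower chance agreement.**
- The ward nurse is called at activation, so the symptom may already have been treated by the 60-minute visit. With p_D = 0.90 and p_N = 0.50 (assumed), Pe = 0.45 + 0.05 = 0.50, and concordance cannot exceed 1 − |0.90 − 0.50| = 60%.
- If recommendations are compared by content, with four categories at shares 0.1, 0.4, 0.3 and 0.2 in both sources (assumed), Pe = 0.01 + 0.16 + 0.09 + 0.04 = 0.30.

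**Step 5. Whether the ICC fills the gap.** The plan does not name the model's outcome.
- If it is the concordant/discordant indicator, a subject effect measures how far concordance clusters within patients. A simulation of 30 patients with 3 activations and no clustering, using a one-way ANOVA ICC as a stand-in for the logistic one, gave a mean ICC of −0.003 at both 50% and 90% concordance.
- If it is the recommendation itself, no stated term links the two recommendations of one activation, so agreement within an episode is mixed with similarity across a patient's episodes.

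Neither reading yields a direction.

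**The case against.** A reader might infer that both sources will mostly say 'give', that chance agreement is therefore high, and that the activation rule alone would produce a good result. The documents do not support this. No 'give' share appears anywhere. The word binary may describe only whether each pair was concordant, with the recommendations themselves differing by drug or action. Step 4 shows that the 60-minute gap could even depress concordance. This part of the objection stands, and the size of the chance problem must be stated conditionally.

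It can also be said that activation on symptoms is the intended use. That is right: measuring agreement there is no flaw in itself. It does mean that the figure cannot be interpreted without the two sources' marginal shares.

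Discrepancies are already graded for potential harm under secondary criterion 4, and the descriptive analysis covers qualitative variables by counts and percentages. The grading is a real mitigation, but a partial one. It is secondary, it gives severity without a stated direction, and it looks only at discordant episodes, so it cannot show how often INSAMED withholds when the nurse does. The descriptive plan does not promise a cross-table of the two recommendations.

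Finally, this is a pilot with no formal test, and INSAMED's output does not affect care. That lowers the stakes. It does not help the reader interpret the headline, and a descriptive cross-table suits a pilot.

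**Conclusion.** The point holds in conditional form. The text establishes three things: a single undirected concordance measure, taken only at symptom-triggered activations, with an analysis that supplies neither a chance correction nor a direction. The loss of direction needs no assumption about shares.

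The chance component depends on quantities that the documents do not give. Under give/withhold scoring with equal, independent shares it runs from 50% agreement at a share of 50% to 90.5% at a share of 95%. It would be lower under comparison by content or a reduced nurse share at 60 minutes. As written, the plan would not let a reader find out which case applies. This is a worthwhile and cheap improvement to reporting; it does not show that the design is invalid.

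**What to change.** Keep the concordance rate. State the recommendation categories and what counts as concordant, and report alongside the rate, as part of the primary result, the cross-table of INSAMED by research-nurse recommendation with:
- agreement among episodes where the nurse would give;
- agreement among episodes where the nurse would not give;
- the two discordance rates separately, as shares of all paired activations.

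Each needs a 95% CI that allows for clustering by patient. A chance-corrected measure with a patient-clustered interval may be added. Among episodes where both say 'give', report same-medication agreement as a prespecified breakdown. Making it a condition for concordance would redefine the endpoint.

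**Cost.** SAP wording and one table; both recommendations are already collected. The row where the nurse would not give may be thin. With 90 activations (assumed) and a nurse 'give' share of 90-95%, it holds 90 × 0.10 = 9 down to 90 × 0.05 = 4.5 episodes. At 9 episodes and 50% agreement, the approximate half-width is 1.96 × √(0.25/9) = 0.33, before any clustering within patients. The headline may also look less favourable. A wide interval there would still tell the reader how little the pilot says about withholding.

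### The research nurse's reference recommendation is made 60 minutes after activation and is not tied to the patient's state at activation, so concordance and harm grading can mix elapsed time with device error

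*Combined protocol and SAP*

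**What the plan says.** Under Secondary Evaluation Criteria, item 1, the two calls are made together: "The patient will simultaneously contact the ward nurse (call bell) and activate INSAMED, which will record the time of request". Practical Conduct of the Study (Vx) gives the purpose of the call: "Call to the ward nurse for effective symptom management".

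The device output follows directly from activation (Investigational Medical Device): "The device then asks the patient questions via the visual interface, to which the patient responds. The device subsequently issues a recommendation". Meanwhile care is not held back (Practical Conduct of the Study): "The patient will be managed according to routine care recommendations, without consideration of INSAMED recommendations".

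The reference is set in the same Vx list: "Visit by the research nurse (without access to INSAMED) 60 minutes after activation; the device sends an email alert upon activation". Its basis is given as "Recommendation based on a standard medical symptom treatment algorithm, medical prescriptions, and patient interview". The Primary Evaluation Criterion says only that the professional's recommendation "will be determined after receipt of an activation message from the device", with no interval and no reference time.

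The primary endpoint is the "Rate of concordance between the recommendations provided by the INSAMED computerized tool and those established by healthcare professionals". Statistical Methods analyses it through an ICC from a logistic model with a random subject effect. That section has no rule, covariate or stratum for episodes treated before the research nurse arrives.

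**The concern.** An as-needed recommendation depends on how the patient feels now and on what has already been given. Within an hour of a call for treatment, the symptom, the doses given and the time since the last dose may all have changed. If the research nurse works from the situation at the visit, the two recommendations answer different questions in those episodes.

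The error can run both ways. A sound device recommendation to treat is scored discordant if the patient has since been treated and the nurse now sees no need. An unsound device recommendation to do nothing is scored concordant for the same reason. Secondary criterion 4 grades only the discrepancies between device and research nurse, so it would grade the false ones and never see the masked ones. The extent also depends on how fast the ward responds, which is itself secondary criterion 1.

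**Working it through.** **Step 1. Order of events, from the documents.**

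| Time | Event | Where stated |
|---|---|---|
| 0 | Patient activates INSAMED and rings for the ward nurse | Secondary Evaluation Criteria, item 1 |
| Just after 0 | On-screen questions, then the INSAMED recommendation | Investigational Medical Device |
| 0 to 60 min | Routine care; treatment may be given | Practical Conduct of the Study |
| 60 min | Research nurse's interview and recommendation | Practical Conduct of the Study, Vx |

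No section asks the research nurse to reconstruct the state at time 0 or to disregard what was given since.

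**Step 2. Effect on the concordance rate.** The plan has no figure to reproduce here: it states no expected concordance and no expected administration delay. Let c be concordance when both recommendations refer to the same state, f the share of episodes whose state has changed by the visit, and c2 the concordance in those episodes. All three are assumptions. Then

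observed concordance = (1 − f)·c + f·c2,

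and observed minus c = f·(c2 − c). The shift is zero if f = 0, downward if c2 < c and upward if c2 > c. The documents therefore fix neither its size nor its sign.

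**Step 3. A device that is perfect at activation.** Let q be the share of episodes treated before the visit and r the share of those in which the nurse's recommendation changes as a result. With c = 1, c2 = 0 and f = q·r, the ceiling is 1 − q·r:

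| q | r | 1 − q·r |
|---|---|---|
| 0.5 | 0.25 | 1 − 0.125 = 87.5% |
| 0.7 | 0.5 | 1 − 0.35 = 65% |
| 0.9 | 0.75 | 1 − 0.675 = 32.5% |

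**Step 4. A device with same-state concordance of 90%** (c = 0.9, assumed):

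| f | c2 = 0 | c2 = 0.5 |
|---|---|---|
| 0.25 | 0.675 + 0 = 67.5% | 0.675 + 0.125 = 80% |
| 0.50 | 0.45 + 0 = 45% | 0.45 + 0.25 = 70% |
| 0.75 | 0.225 + 0 = 22.5% | 0.225 + 0.375 = 60% |

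**Step 5. Scale.** If 30 independent episodes gave 27 concordant (90%), the Wilson 95% interval would be 74.4% to 96.5%. The 80% value in Step 4 lies inside that interval; the other five lie below it. The shift can therefore exceed sampling error, but need not.

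Steps 2 to 5 are on the concordance-rate scale. No effect on the planned ICC has been derived.

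**The case against.** A reader might infer that the endpoint always compares two different clinical states. The documents do not support that. The symptom may be unchanged and treatment may not have been given by 60 minutes. The patient interview could also be meant to look back to activation, and linking the recommendation to the activation message is compatible with that. The text is a study summary, so its silence on nurse instructions weighs less than silence in a full procedures section would. What stands is that no retrospective reading is written, and a nurse who follows the schedule literally can judge the later state.

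A reader might also infer that the delay is pointless because the alert is sent at once. That does not hold either. The research nurse records the time to administration (criterion 1), and satisfaction with the ward nurse's response (criterion 2) can be measured only after that response. A later visit plausibly serves both.

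Nor can one infer that the device will look worse than it is, or by how much: the direction is open, and q, r, f and c2 are not in the documents.

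Finally, this is a single-centre pilot with no formal test and no stated concordance threshold, and the device output does not reach the treating nurse. What is at risk is the interpretation of the results, not patient care. Even so, concordance is how this pilot judges feasibility, and a result that cannot separate device error from elapsed time does not serve that aim.

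**Conclusion.** The concern holds in a limited form. The time gap and the missing reference time are in the text. In episodes where treatment was given or the symptom changed within the hour, the primary concordance and the criterion 4 grading can confuse elapsed time with device error, in either direction. How often this happens, and its net effect, cannot be computed from the documents. The range of 87.5% to 32.5% assumes a device perfect at activation and chosen values of q and r; it shows that the effect could matter, and predicts nothing. The point should be settled before data collection, because a reference state that is not recorded at the time cannot be reliably recovered afterwards.

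**What to change.** Keep the 60-minute visit. State in the Primary Evaluation Criterion and in Vx that the research nurse issues the reference recommendation for the patient's state at the activation timestamp. It should use symptom intensity as it was at activation and the prescriptions and medication chart as of that time, disregarding anything given afterwards. This concerns the reference recommendation only; routine care is unchanged.

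In Statistical Methods, use the request and administration times already collected for criterion 1 to flag episodes treated before the visit. Report concordance separately for treated and untreated episodes as a supportive analysis, noting that untreated episodes are selected for slow or no ward response and may be few.

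Having the research nurse attend before any ward treatment is not recommended. Arrival ahead of a ward nurse called at the same moment cannot be guaranteed, and making treatment wait would depart from routine care and distort criterion 1.

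The cost is wording in the procedure, the case report form and the analysis section. The downside is up to 60 minutes of symptom recall. Recall affects symptom intensity; earlier doses can be read from the chart.

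### Masking of the research nurse is not secured: the plan blocks her access to INSAMED but not disclosure of its output by the patient she interviews

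*Combined protocol and SAP*

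**What the plan says.** The Primary Evaluation Criterion is the "Rate of concordance between the recommendations provided by the INSAMED computerized tool and those established by healthcare professionals". For the professional's side of each pair, "a research nurse (RN) will generate a recommendation based on the medical algorithm for symptom management, medical prescriptions, and patient interview, without consulting INSAMED". Statistical Methods confirms that the research nurse is the comparator.

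Practical Conduct of the Study (Vx) gives the timing: "Visit by the research nurse (without access to INSAMED) 60 minutes after activation; the device sends an email alert upon activation". Before that visit the patient has activated the device, called the ward nurse and answered the device's questions.

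Under Investigational Medical Device, INSAMED is described in these terms: "It consists of a patient interface designed to assist patients with the administration of “as needed” medications in the postoperative period". Once the patient has answered, "The device subsequently issues a recommendation". The same section adds: "This recommendation is not communicated to the ward nurse responsible for patient care". The Primary Evaluation Criterion says that the device's recommendations are retrieved for analysis from its usage history.

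**The concern.** Concordance is informative only if the two recommendations are formed independently. The plan recognises this by keeping the research nurse away from the device. It closes only the direct route, however. One of her three sources is the patient, who by then has used a patient-facing tool that has produced an answer.

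If the patient has seen that answer and mentions it, the nurse may move towards it. Two endpoints would be affected:

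- **Primary endpoint.** Pairs that would have disagreed now agree, so concordance rises.
- **Harm grading (secondary criterion 4).** Only discrepancies between INSAMED and the research nurse are graded. A discrepancy removed by disclosure is never graded, so the tool could look safer as well as more accurate.

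Two further effects are possible, also only if the patient sees the output. The patient could relay it to the ward nurse, although care is meant to take no account of INSAMED. The patient's satisfaction score, which is analysed by agreement between INSAMED and the nurse's response, could reflect knowledge of that agreement.

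**Working it through.** **1. Which routes from the device to the reference does the text close?**

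| Route | Text | Status |
|---|---|---|
| Research nurse consults the device | Barred in the Primary Evaluation Criterion and again under Vx | Closed |
| Device output passed to the ward nurse | Barred under Investigational Medical Device | Closed as a direct route, but she does not supply the primary reference |
| Patient tells the research nurse at interview | No instruction to patient or nurse | Not closed |
| Alert email at activation | Content not described | Not stated |
| Output on the patient's screen | Device issues a recommendation; display not mentioned | Not stated |
| Record of unmasking, or analysis allowing for it | None | Absent |

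**2. Is there a figure in the plan to reproduce?** No. The 30 users are a pragmatic number, with no expected concordance or precision target, and the plan gives no rate of disclosure. What follows is an illustration on assumed inputs.

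**3. Size of the upward effect.** Let p be concordance under full masking, and L the share of otherwise discordant episodes in which the nurse switches to the device's answer. Both are assumptions.

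Observed concordance = p + (1 − p) × L, so the inflation is (1 − p) × L.

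| p | L = 10% | L = 25% | L = 50% | Inflation (points) |
|---|---|---|---|---|
| 0.70 | 0.73 | 0.775 | 0.85 | 3 to 15 |
| 0.80 | 0.82 | 0.85 | 0.90 | 2 to 10 |
| 0.90 | 0.91 | 0.925 | 0.95 | 1 to 5 |

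L can be split into the share of interviews with disclosure and the share of discordant cases in which the nurse then adopts the output. With adoption fixed at one half and p = 0.80:

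- disclosure in 25% of interviews: 0.25 × 0.5 × 0.20 = 0.025, or 2.5 points;
- disclosure in every interview: 1.0 × 0.5 × 0.20 = 0.10, or 10 points.

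In this model L is also the share of discrepancies lost from the harm grading: 10% to 50%.

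**4. Would the data reveal it?** Take one episode for each of 30 users. The Wilson 95% interval at 0.80 runs from 0.627 to 0.905, which contains 0.82, 0.85 and 0.90. The simple half-width is 1.96 × √(0.8 × 0.2 / 30) = 0.143 at 0.80, and 1.96 × √(0.9 × 0.1 / 30) = 0.107 at 0.90. The 10-point bias comes close to the 10.7-point half-width only if every interview leaks. Repeated activations would change these widths, and the planned ICC is on another scale, so they are orientation only.

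**5. The opposite effect.** The ward nurse is called at activation, so the patient may have been treated, and the symptoms may have changed, before the interview. Let D be the share of otherwise concordant episodes made discordant in this way. It cancels disclosure when p × D = (1 − p) × L, so D = (1 − p) × L / p. At p = 0.80:

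- L = 10%: D = 0.02 / 0.80 = 2.5%
- L = 25%: D = 0.05 / 0.80 = 6.25%
- L = 50%: D = 0.10 / 0.80 = 12.5%

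Modest values of D are enough to offset disclosure, so the sign of the net bias cannot be settled from the documents.

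**The case against.** The plan states the nurse's masking twice, and nowhere does it say that the recommendation is displayed to the patient. Retrieval from the usage history is compatible with silent logging. A reader might infer that the reference is not blind and that concordance is therefore inflated. The documents do not support either step: display is the natural reading of a device meant to assist patients, but it remains an inference, and the 60-minute gap can push concordance down.

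A reader might also take the ward-nurse sentence as proof of a leak into the primary endpoint. It is not, because the research nurse supplies the reference. The sentence only shows how narrow the explicit rule is.

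Other points count in the plan's favour. The available text is a study summary. Training at V0 and the reminders at V1 and V3 are listed without their content, so a non-disclosure instruction could exist there. The nurse also works from an algorithm and the prescriptions, which limits her room to be swayed, and nothing in the documents supports adoption in half of discordant cases. This is a pilot without a hypothesis test, and INSAMED does not direct care.

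All of this limits the strength of the claim and the weight of the figures. It does not close the route: the text still relies on an interview with a patient who has used the device, and provides neither a safeguard nor a record if masking fails. An accidental offset from delayed interviews would be a second error of unknown size and would not restore masking.

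**Conclusion.** The point holds in a limited form. The research nurse's masking covers direct access only, and the independence of the primary comparison and of the harm grading is not protected against disclosure by the patient. Whether disclosure would occur is unknown, because the plan does not say whether the patient sees the output.

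If it occurs, disclosure itself acts towards agreement: about 2 to 10 points at an assumed 80% concordance with 10% to 50% of discordant episodes switched. These inputs are assumptions and nothing in the plan fixes them. Net bias, once the 60-minute gap is allowed for, is of unknown size and direction. The satisfaction and ward-care effects depend on the same unstated display and are secondary.

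This is a cheap improvement worth making before data collection, since lost independence cannot be recovered afterwards. It does not show that the endpoint is invalid.

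**What to change.** State in the protocol whether the patient sees the recommendation. Then:

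1. At V0, V1 and V3, instruct patients not to disclose INSAMED's output, and instruct the research nurse not to ask for it.
2. State that the activation email carries no recommendation.
3. Add a tick box to the case report form: did the nurse learn the output before recording her own recommendation?
4. Report the frequency of disclosure, and repeat the concordance and harm-grading analyses without the disclosed activations.
5. Where the prototype allows, withhold the output on screen until the nurse's recommendation is time-stamped. The analysis does not need it on screen, because it comes from the usage history.

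Items 1 to 4 cost a line of training, one form field and one sensitivity analysis. That analysis loses some episodes, and it relies on the nurse reporting disclosure accurately. Item 5 is the stronger protection, but the documents do not say how configurable the prototype is, and the ease-of-use score would then rate a version with delayed output. None of these items removes the effect of treatment during the 60 minutes, which should be acknowledged when concordance is interpreted.
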